#### **5.3.4 Luteinizing hormone-releasing hormone (LHRH) agonist (e.g., goserelin, leuprolide)**

Commercially available luteinizing hormone-releasing hormone (LHRH) agonist (goserelin or leuprolide) will be used. Locally obtained commercial supplies will be used in accordance with local regulations only for premenopausal women.

### **5.4 Dose Modifications**

- The following dose modifications were developed from the FDA label and supplemented by additional participant-oriented modifications used in previous clinical trials.
- Grading is according to CTCAE Version 5.0.
- All treatment should be discontinued/delayed until the toxicity resolves to Grade 1 or lower, or to baseline if Grade 2 at the time of study entry
- Patients may delay retreatment for up to 28 days to allow the toxicity to resolve. If the toxicity requiring dose interruption has not resolved completely or to CTCAE Grade 1 (or to baseline if Grade 2 at time of study entry) during the maximum 28-day dose interruption period, the patient must permanently discontinue treatment on study
- Patients may restart therapy if toxicities resolve to Grade 1 or lower (or to baseline if Grade 2 at the time of study entry).
- If a dose interruption is required at any point on the study because of hematologic toxicity, weekly blood draws for CBC will be monitored until the AE resolves, and weekly blood draws for CBC also will be required for an additional 4 weeks after the AE has been resolved to the specified levels.
- The patient must be referred to a hematologist for further evaluation (1) if frequent transfusions are required or (2) if the treatment-related hematologic toxicities have not recovered to CTCAE Grade 1 or less after 28 days.
- For major surgery while on treatment, up to 28 days of study treatment interruption is allowed.
- All dose interruptions (including any missed doses), and the reasons for the reductions/interruptions, are to be recorded.

Table 5: Dose Modification and Management for Interstitial Lung Disease/Pneumonitis

Interstitial Lung Disease/Pneumonitis	Grade 1 (asymptomatic)	Grade 2 (symptomatic)	Grade 3 (Severe symptomatic) or Grade 4 (life-threatening)
	No dose interruption or adjustment is	Dose interruption until recovery to Grade $\leq 1$ then	Discontinue ribociclib.

	required. Initiate appropriate medical therapy and monitor as clinically indicated	consider resuming ribociclib at the next lower dose level*. If Grade 2 recurs, discontinue ribociclib.	

*An individualized benefit-risk assessment should be performed when considering resuming ribociclib.
			

Table 6: Dose Modification and Management for cutaneous adverse reactions including SCARs

Grade 1 (< 10% body surface area (BSA) with active skin toxicity, no signs of systemic involvement)	Grade 2 (10-30% BSA with active skin toxicity, no signs of systemic involvement)	Grade 3 (severe rash not responsive to medical management; > 30% BSA with active skin toxicity, signs of systemic involvement present; SJS*)	Grade 4 (any % BSA associated with extensive superinfection, with IV antibiotics indicated; life threatening consequences; TEN**) )
No dose adjustment is required.  Initiate appropriate medical therapy and monitor as clinically indicated.		Interrupt ribociclib until the etiology of the reaction has been determined.  If the etiology is a SCAR, permanently discontinue ribociclib. If the etiology is not a SCAR, interrupt dose until recovery to Grade $\leq$ 1, then resume ribociclib at the same dose level. If the cutaneous adverse reaction still recurs at Grade 3, resume ribociclib at the next lower dose level.	Permanently discontinue ribociclib.

Abbreviations: Severe Cutaneous Adverse Reactions (SCARs); Stevens-Johnson Syndrome (SJS); Toxic Epidermal Necrolysis (TEN)
 
* SJS (Grade 3 and 4) is defined as skin sloughing covering <10% BSA and 10-30% BSA, respectively, with associated signs (e.g., erythema, purpura, epidermal detachment and mucous membrane detachment)
 
** TEN (Grade 4) is defined as skin sloughing covering <math>\geq</math>30% BSA with associated symptoms (e.g., erythema, purpura, epidermal detachment, and mucous membrane detachment).
			

Table 7: Dose Modification and Management for QT Prolongation

ECGs with QTcF* > 480 ms	
 
Interrupt ribociclib treatment ms
 
If QTcF prolongation resolves to < 481 ms, resume treatment at the next lower dose
 
If QTcF <math>\geq</math> 481 ms recurs, interrupt dose until QTcF resolves to < 481 ms; then resume ribociclib at next lower dose level.
 

ECGs with QTcF* > 500 ms	
 
Interrupt ribociclib treatment if QTcF greater than 500 ms
 
If QTcF prolongation resolves to < 481 ms, resume treatment at the next lower dose level.
 
 
Permanently discontinue ribociclib if QTcF interval prolongation is either greater than 500 ms or greater than 60 ms change from baseline AND associated with any of the following: Torsades de Pointes, polymorphic ventricular tachycardia, unexplained syncope, or signs/symptoms of serious arrhythmia.


Electrocardiograms (ECGs) should be assessed prior to initiation of treatment. Repeat ECGs at approximately Day 14 of the first cycle and at the beginning of the second cycle, and as clinically indicated.
 
*QTcF = QT interval corrected by Fridericia's formula.
	

Table 8: Dose Modification and Management for AST or ALT Elevations

	Grade 1 (> ULN – 3x ULN)	Grade 2 (> 3 to 5x ULN)	Grade 3 (>5 to 20x ULN)	Grade 4 (> 20x ULN)
AST and/or ALT elevations from baseline*, WITHOUT total bilirubin increase above 2x ULN	No dose adjustment required	Baseline* at < Grade 2: Dose interruption until recovery to ≤ baseline grade, then resume ribociclib at same dose level. If Grade 2 recurs, resume ribociclib at next lower dose level Baseline* at Grade 2: No dose interruption	Dose interruption until recovery to ≤ baseline* grade, then resume at next lower dose level. If Grade 3 recurs, discontinue ribociclib.	Discontinue ribociclib
Combined elevations in AST and/or ALT WITH total bilirubin increase, in the absence of cholestasis	If patients develop ALT and/or AST > 3 x ULN along with total bilirubin > 2 x ULN irrespective of baseline grade, discontinue ribociclib.			
Abbreviations: AST, aspartate aminotransferase; ALT, alanine aminotransferase; ULN, upper limit of normal. *Baseline = prior to treatment initiation.				

Table 9: Dose Modification and Management for Blood bilirubin increased without AST/ALT increase

Toxicity/Grade	Recommendations
Blood bilirubin increased without AST/ALT increase	
Grade 1: >ULN - 1.5 x (upper limit of normal) ULN if baseline was normal; > 1.0 - 1.5 x baseline if baseline was abnormal	Maintain dose level with LFTs monitored bi- weekly.
Grade 2: >1.5 - 3.0 x ULN if baseline was normal; >1.5 - 3.0 x baseline if baseline was abnormal	Dose interruption of ribociclib. If resolved to ≤ grade 1 in ≤ 21 days, then maintain dose level. If resolved to ≤ grade 1 in > 21-28 days or toxicity recurs, then reduce 1 dose level. Repeat liver enzyme and bilirubin tests twice weekly for 2 weeks after dose resumption. If toxicity recurs after two dose reductions, or recovery to ≤ grade 1 is > 28 days, discontinue ribociclib.
Grade 3: >3.0 - 10.0 x ULN if baseline was normal; >3.0 - 10.0 x baseline if baseline was abnormal	Dose interruption of ribociclib, until resolved to ≤ grade 1, then lower 1 dose level of ribociclib. Repeat liver enzyme and bilirubin tests twice weekly for 2 weeks after dose resumption. If resolved to ≤ grade 1 in > 28 days or toxicity recurs, discontinue ribociclib.
Grade 4: >10.0 x ULN if baseline was normal; >10.0 x baseline if baseline was abnormal	Discontinue ribociclib.

Table 10: Dose Modification and Management for Neutropenia

Grade 1 or 2 (ANC 1000/mm  to LLN)	Grade 3 (ANC 500 to 1000/mm  )	Grade 3 Febrile Neutropenia	Grade 4 (ANC < 500/mm  )
No dose adjustment required	Dose interruption until recovery to Grade $\leq$ 2. Resume ribociclib at the same dose level. If toxicity recurs at Grade 3, dose interruption until recovery, then resume ribociclib at the next lower dose level.	Dose interruption until recovery of neutropenia to Grade $\leq$ 2. Resume ribociclib at the next lower dose level.	Dose interruption until recovery to Grade $\leq$ 2. Resume ribociclib at the next lower dose level.
Abbreviations: ANC, absolute neutrophil count; LLN, lower limit of normal. *Grade 3 neutropenia with single episode of fever $> 38.3^{\circ}\text{C}$ (or) above $38^{\circ}\text{C}$ for more than one hour and/or concurrent infection.			

Table 11. Dose modifications and Management for Thrombocytopenia and Anemia

Toxicity/Grade	Recommendations
Thrombocytopenia (platelet count)	
Grade 1: <75,000 mm 	No dose adjustment required
Grade 2: 50-75 mm 	Dose interruption until recovery to grade $\leq$ 1. Re- initiate ribociclib at the same dose.
Grade 3: 25-50 mm 	Dose interruption until recovery to grade $\leq$ 1. Re- initiate ribociclib at the same dose level. If toxicity recurs at grade 3: temporary dose interruption until recovery to grade $\leq$ 1 and reduces ribociclib to the next lower dose level.
Grade 4: >25 mm 	Dose interruption until recovery to grade $\leq$ 1. Re- initiate ribociclib at the next lower dose level. If toxicity recurs at grade 4: discontinue ribociclib.
Anemia (hemoglobin)	
Grade 1: $\geq 10.0$ – LLN g/dL	No dose adjustment required.
Grade 2: $\geq 8.0$ – $< 10.0$ g/dL	No dose adjustment required.
Grade 3: $< 8.0$ - $> 4.9$ g/dL, transfusion indicated	Dose interruption until recovery to grade $\leq$ 2. Re- initiate ribociclib at the same dose.
Grade 4: Life-threatening consequences; urgent intervention indicated	Discontinue ribociclib.

Table 12: Dose Modification and Management for Other Toxicities that are deemed  
related and clinically significant by the treating physician\*

Grade 1 or 2	Grade 3	Grade 4
--------------	---------	---------

No dose adjustment is required. Initiate appropriate medical therapy and monitor as clinically indicated	Dose interruption until recovery to Grade $\leq 1$ then resume ribociclib at same dose level. If Grade 3 recurs, resume ribociclib at the next lower dose level.	Discontinue ribociclib.
--	---	-------------------------

\*Excluding adverse reactions discussed in tables 5-11.

Table 13. Dose Modifications for Toxicities Related to Ribociclib

Starting dose	600 mg
First dose reduction	400 mg
Second dose reduction	200 mg

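### Section 5.4's general rule restarts treatment at Grade 1 or lower, while Tables 10 and 11 restart after neutropenia and Grade 3 anemia at Grade 2 or lower, and nothing says which governs

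*Combined protocol and SAP*

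**What the plan says.** Section 5.4 opens with general bullets, then gives toxicity-specific tables.

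The bullets set one recovery level and use it three times:
- Hold: "All treatment should be discontinued/delayed until the toxicity resolves to Grade 1 or lower", with an exception allowing return to baseline for patients who were at Grade 2 on entry.
- Restart: the same level, with the same exception.
- Time limit: if that level is not reached "during the maximum 28-day dose interruption period, the patient must permanently discontinue treatment on study".

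A further bullet applies Grade 1 to blood toxicities by name. Referral to a hematologist is required "if the treatment-related hematologic toxicities have not recovered to CTCAE Grade 1 or less after 28 days".

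The tables set a different level for two toxicities. For Grade 3 neutropenia, Table 10 reads "Dose interruption until recovery to Grade $\leq$ 2. Resume ribociclib at the same dose level". The Grade 3 febrile column ("Dose interruption until recovery of neutropenia to Grade" 2 or lower) and the Grade 4 column use the same recovery level, with a dose reduction. Table 11 resumes at Grade 2 or lower after Grade 3 anemia.

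The only statement of scope attached to the tables is the footnote to Table 12, which excludes reactions covered by Tables 5 to 11. It does not mention the general bullets.

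**The concern.** These are two explicit instructions for the same clinical situation, and they cannot both be followed. The bullets are worded for all toxicities and the 28-day rule is mandatory. The tables are equally explicit.

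Neutropenia is where this matters most. Section 1.2.4 describes it as the most commonly reported adverse event in MONALEESA-3 and the most common reason for dose adjustments and interruptions in MONALEESA-2. With four participating centers, sites could reasonably read section 5.4 in different ways. Patients in the same state would then be handled differently, and actual dosing in cycle 1 would vary for reasons unrelated to the patient.

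**Working it through.** The plan states no figure to reproduce, so the check sets the passages side by side and compares their timing with the study calendar.

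**Step 1: recovery level for resuming ribociclib.**

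| Event | General bullets, 5.4 | Toxicity table | Same level? |
|---|---|---|---|
| Grade 3 neutropenia | Grade 1 or lower, or baseline if Grade 2 at entry | Grade 2 or lower (Table 10) | No |
| Grade 3 febrile neutropenia | as above | Grade 2 or lower (Table 10) | No |
| Grade 4 neutropenia | as above | Grade 2 or lower (Table 10) | No |
| Grade 3 anemia | as above | Grade 2 or lower (Table 11) | No |
| Grade 2-4 thrombocytopenia | as above | Grade 1 or lower (Table 11) | Yes, apart from the baseline exception |

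The mismatch is confined to neutropenia and Grade 3 anemia. The bullets also speak of all treatment, whereas the tables address ribociclib only.

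**Step 2: who is caught.** Entry requires hemoglobin of at least 8 g/dL (section 3.3), and Table 11 defines Grade 2 anemia as 8.0 to below 10.0 g/dL. A patient can therefore enter at Grade 2, and for her the baseline exception brings the two rules together. Entry also allows a neutrophil count of 1,200/mm³. Table 10 pools Grades 1 and 2 (1,000/mm³ to the lower limit of normal), so whether such a patient counts as Grade 2 is not settled by the protocol text. The conflict is clear for patients at Grade 0-1 at entry whose event has come down to Grade 2 and no further.

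**Step 3: can it arise on study?** The scheduled on-treatment blood count is on days 8-16. Section 5.4 then requires weekly counts after a hematologic hold, so the next count falls on day 8 + 7 = 15 to day 16 + 7 = 23. Dosing runs to day 21. The restart question can therefore arise within cycle 1, and again when cycle 2 is due.

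**Step 4: can the 28-day limit expire on study?** A hold starting at the scheduled count reaches its limit on day 8 + 28 = 36 to day 16 + 28 = 44. The final visit is day 29 ± 3, so day 32 at the latest. To expire by then, the hold must begin by day 32 − 28 = 4, before any scheduled on-treatment count.

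**Step 5: PK visit.** Serial sampling and the first scheduled on-treatment count share the day 8-16 window. A toxicity found on schedule would normally be found at about the time of sampling. Both rules also require the initial hold for Grade 3-4 neutropenia; they differ only on when it ends.

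**The case against.** The strongest reply is that specific tables ordinarily override general text, and that the weekly-count bullet's mention of resolution to specified levels may point to the tables. That is a natural reading, but the protocol does not state it, and the hematologist-referral bullet applies Grade 1 to blood toxicities directly. Nor would precedence settle everything. Table 10 and the Grade 3 anemia row carry no time limit of their own, unlike Table 9. The general 28-day rule, tied to Grade 1, is then the only limit, and a site could not tell whether it applies to a patient still at Grade 2 on day 28.

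The objections to larger consequences do stand:
- **Number affected.** A reader might infer that 13 to 22 of 36 patients are affected, from 0.74 × 0.49 × 36 = 13 (MONALEESA-2, taking 49% as a share of the 74% with neutropenia) and 0.61 × 36 = 22 (MONALEESA-7). The documents do not support this. The two ends use different denominators. The rates cover all grade 3/4 neutropenia and are not limited to one cycle, and median time to first dose reduction in MONALEESA-2 was 2.9 months. They are not restricted to patients at Grade 0-1 at entry who are at Grade 2 when restart is decided.
- **Primary endpoint.** A reader might infer that the conflict decides who is on drug at the PK visit. Given the shared window, that would take an earlier unscheduled count, a hold and recovery to exactly Grade 2 before sampling.
- **Evaluability.** A reader might infer that held patients become non-evaluable. Section 4.3.13 refers to inability to tolerate ribociclib or to take part in the laboratory and cardiac work-up; it names neither a hold nor a recovery grade.
- **Permanent discontinuation.** The wording conflicts, but the limit would rarely be reached before protocol follow-up ends and treatment passes to the treating physician.

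**Conclusion.** The contradiction stands on the wording. Section 5.4 gives two different recovery levels for resuming ribociclib after Grade 3, Grade 3 febrile or Grade 4 neutropenia and after Grade 3 anemia, with no order of precedence. It affects patients at Grade 0-1 at entry who have recovered only to Grade 2, within cycle 1 or at the start of cycle 2. For patients at Grade 2 at entry the rules can agree.

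Its size cannot be stated: the documents give no cycle 1 frequency for this subset. The effect on the PK visit is likely small and expiry of the 28-day limit on study would be rare. Both judgments assume that toxicities are found at the scheduled counts. The point is one of safety instructions and consistency across sites. It is not evidence that the primary comparison is compromised. No view is taken on which recovery level is right.

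**What to change.** In section 5.4:
1. Reconcile the general hold and restart bullets with Tables 10 and 11.
2. State which governs when a toxicity-specific table exists.
3. Make the 28-day discontinuation rule and the hematologist-referral bullet refer to the same recovery level as the governing rule.

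The sponsor decides the level. The cost is a sentence or two of text in an amendment, with a notice to sites. Sample size, assessments and analysis are unchanged.

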- Documented HER2-negative tumor based on local testing on most recent tumor biopsy: HER2-negative tumor is determined as immunohistochemistry score 0/1+ or negative by in situ hybridization (FISH/CISH/SISH) defined by current ASCO/CAP (American Society of Clinical Oncology/College of American Pathologists) guidelines. Patients with equivocal HER2 in situ hybridization results according to current ASCO/CAP guidelines are eligible, as long as they have not received and are not scheduled to receive anti-HER2 treatment.
- Must be capable of understanding and complying with parameters as outlined in the protocol and able to sign and date the informed consent, approved by the IRB, prior to the initiation of any screening or study-specific procedures.
- Patient must be able to swallow ribociclib tablets.
- Patient must be able to communicate with the investigator and comply with the requirements of the study procedures. (Note: Communication through an interpreter is acceptable)
- Patient has adequate bone marrow and organ function as defined by the following laboratory values:
  - Absolute neutrophil count (ANC)  $\geq 1,200/\text{mm}^3$ ; Patients must be able to meet the criteria without receipt of colony stimulating factors within 2 weeks before obtaining sample
  - Platelets  $\geq 100,000/\text{mm}^3$ ; Patients must be able to meet the criteria without receipt of transfusion within 2 weeks before obtaining sample
  - Hemoglobin  $\geq 8 \text{ g/dL}$ ; Patients must be able to meet the criteria without receipt of transfusion within 2 weeks before obtaining sample
  - Estimated glomerular filtration rate (eGFR)  $\geq 30 \text{ mL/min/1.73m}^2$  according to the CKD EPI equation (**Note:** if the eGFR is not calculated from the serum creatinine using CKD EPI equation, please enter the most recent data into this calculator: [https://www.kidney.org/professionals/kdoqi/gfr\\_calculator](https://www.kidney.org/professionals/kdoqi/gfr_calculator))
  - Total bilirubin  $< \text{ULN}$  except for patients with Gilbert's syndrome who may only be included if the total bilirubin is  $\leq 3.0 \times \text{ULN}$  or direct bilirubin  $\leq 1.5 \times \text{ULN}$ .
  - Aspartate transaminase (AST)  $< 2.5 \times \text{ULN}$ , except for patients with liver metastases, who are only included if the AST is  $< 5 \times \text{ULN}$ .

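### Section 5.4 gives conflicting or incomplete dose instructions when AST/ALT is above ULN up to 3x ULN and bilirubin is raised as well

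*Combined protocol and SAP*

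**What the plan says.** Section 5.4 of the combined protocol and SAP handles liver tests in two tables.

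- **Table 8, first row**, covers "AST and/or ALT elevations from baseline*, WITHOUT total bilirubin increase above 2x ULN". For AST/ALT above ULN up to 3x ULN (Grade 1) the instruction is "No dose adjustment required".
- **Table 8, second row**, is headed "Combined elevations in AST and/or ALT WITH total bilirubin increase, in the absence of cholestasis". Its only instruction is: "If patients develop ALT and/or AST > 3 x ULN along with total bilirubin > 2 x ULN irrespective of baseline grade, discontinue ribociclib".
- **Table 9** is restricted, in its title and again in its row heading, to "Blood bilirubin increased without AST/ALT increase". From a normal baseline it interrupts ribociclib at Grade 2 (above 1.5 up to 3x ULN). At Grade 3 (above 3 up to 10x ULN) it interrupts and then lowers the dose one level. At Grade 4 (above 10x ULN) it discontinues.

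Two other parts of Section 5.4 bear on the same patient. The opening bullets hold all treatment until a toxicity is back to Grade 1 or below (or to a Grade 2 baseline). They allow a restart once that happens and require permanent discontinuation if it has not happened within 28 days. Table 12 covers other toxicities that the treating physician judges related and clinically significant, with the footnote "Excluding adverse reactions discussed in tables 5-11".

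**The concern.** A patient with two abnormal liver tests can receive a less restrictive table instruction than a patient with the same bilirubin and normal AST/ALT, or can match no row. The general bullets do not settle this, because the protocol does not say whether they or the tables govern.

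Two sites could act differently on identical results and each point to Section 5.4. The first issue is patient safety and uniform handling. The second is data quality: changes in AST and ALT from baseline to days 8-16 and to the visit before cycle 2 are secondary endpoints (Section 2.4), and inconsistent holding during cycle 1 could carry into the later of these.

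**Working it through.** The protocol states no figure to reproduce, so the check applies the table conditions literally. Assumptions: AST/ALT and bilirubin normal at baseline, and no cholestasis. All values are multiples of ULN.

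**Conditions**

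- Table 8, first row: AST/ALT > 1 and bilirubin ≤ 2.
- Table 8, second row: AST/ALT > 3 and bilirubin > 2.
- Table 9: bilirubin > 1 and AST/ALT ≤ 1.

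**Result by bilirubin band**

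| Bilirubin | AST/ALT not raised (Table 9) | AST/ALT > 1 to 3 (Table 8) |
|---|---|---|
| > 1 to 1.5 | Grade 1: dose maintained | Grade 1: no change |
| > 1.5 to 2 | Grade 2: interrupt | Grade 1: no change |
| > 2 to 3 | Grade 2: interrupt | no row |
| > 3 to 10 | Grade 3: interrupt, then one level lower | no row |
| > 10 | Grade 4: discontinue | no row |

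The last three rows are empty on the right because bilirubin above 2 fails the first row of Table 8, AST/ALT of 3 or less fails the second, and raised AST/ALT fails Table 9.

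**Worked points**

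- Bilirubin 1.8: AST/ALT 0.9 gives interruption; AST/ALT 1.5 or 2.9 gives no dose change.
- Bilirubin 2.5 and 5: AST/ALT 0.9 gives interruption; AST/ALT 1.5 or 2.9 gives no row.
- Bilirubin 12: AST/ALT 0.9 gives discontinuation; AST/ALT 1.5 or 2.9 gives no row.
- AST/ALT 4, 8 or 25: every bilirubin level tried has an instruction. The problem is confined to AST/ALT above 1 up to 3.

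**Do the general bullets close the gap?**

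- *Bilirubin > 1.5 to 2.* This is Grade 2 on Table 9's scale, so the bullets call for a hold, while Table 8 calls for no change. The bullets cannot simply be read as overriding the tables: Table 10 makes no adjustment for Grade 2 neutropenia and Table 12 makes none for Grade 2 events.
- *Bilirubin > 2.* The bullets supply a hold and a stop if the toxicity is unresolved at 28 days. They give no restart dose level, whereas Table 9 does (same level or one lower for Grade 2, depending on recovery time; one lower for Grade 3). Above 10, they allow a restart on resolution where Table 9 discontinues.

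**Does Table 12 close it?** The footnote can be read either way. If bilirubin and AST/ALT elevations count as discussed in the earlier tables, Table 12 is excluded. If this particular combination does not count, Table 12 could apply, with these results:

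- Bilirubin > 2 to 3 (Grade 2): no adjustment, against the general hold and against interruption in Table 9.
- Bilirubin > 3 to 10 (Grade 3): interrupt and resume at the same level, against one level lower in Table 9.
- Bilirubin > 10 (Grade 4): discontinue, as in Table 9.

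Section 8.7 does not help, because its default actions are for events not captured by CTCAE Version 5.0.

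**An undefined term.** Table 9 does not say whether an AST/ALT increase is measured from ULN or from baseline. Section 3.3 admits patients with AST and ALT below 2.5x ULN, even without liver metastases. Take a patient who enters at 2x ULN, stays there, and develops bilirubin of 1.8x ULN from a normal baseline. If the increase is measured from baseline, she falls under Table 9 (interrupt). If it is measured from ULN, she falls outside Table 9, and Table 8 Grade 1 is the row that remains (no change).

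**The case against.** The strongest reply is that no patient is left without direction. Bilirubin above 2x ULN is at least Grade 2 from a normal baseline, so the general bullets hold treatment and stop it permanently if unresolved at 28 days. On one reading of its footnote, Table 12 adds interruption at Grade 3 and discontinuation at Grade 4. The direct conflict in Table 8 is limited to a narrow bilirubin band, above 1.5 up to 2x ULN.

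The practical window is also short. The study covers one cycle in 36 patients, with scheduled on-treatment laboratory checks on days 8-16 and before cycle 2. Ribociclib ends on day 21, so 21 - 16 = 5 to 21 - 8 = 13 days remain after the mid-cycle check for a restart dose to matter within the study. After that, treatment follows standard of care.

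Much of this stands. A reader might infer that patients above 2x ULN have no rule at all; the general bullets show otherwise. What survives is the contradiction without stated precedence, the missing restart level, the difference above 10x ULN, and the unclear reach of Table 12.

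A reader might also infer that an eligible patient could meet the discontinuation row on entry. Section 3.3 admits "patients with Gilbert's syndrome who may only be included if the total bilirubin is" at most 3x ULN (or direct bilirubin at most 1.5x ULN), and patients with liver metastases and AST/ALT below 5x ULN. The documents do not support that inference as a finding. The discontinuation row is conditioned on patients who develop the values, and values present at entry have not developed on treatment. Its clause about baseline grade leaves some doubt over a later small rise, but that is a wording query.

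**Conclusion.** The inconsistency is real and follows from the table text. For AST/ALT above ULN up to 3x ULN, from a normal baseline and without cholestasis:

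- bilirubin above 1.5 up to 2x ULN receives conflicting instructions;
- bilirubin above 2x ULN receives only the general hold and 28-day rule, with no table row that clearly applies.

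How often this would arise cannot be stated. A reader might take the transaminitis figures in Section 1.2.4 (15%, mostly Grade 1 or 2, in MONALEESA-2; 12% in MONALEESA-7) as a guide. They describe raised transaminases, not the combination with bilirubin, and they are not first-cycle rates. Counting the table combinations that fail is not a frequency either. The combined pattern is uncommon, and the documents give no rate for it.

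Sample size and power are unaffected, and no effect on the primary AUC comparison is shown. An effect on the secondary AST/ALT data is possible but unquantified. The point merits correction because it concerns safety instructions and is cheap to fix; it does not threaten the trial's main conclusion.

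**What to change.** Reconcile Table 8, Table 9, the Table 12 footnote and the opening bullets of Section 5.4 so that each combination of AST/ALT and bilirubin level falls under exactly one instruction. Specifically:

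- state which table governs when AST/ALT and bilirubin are both raised, and whether the general bullets or the tables take precedence;
- state whether Table 12 can apply to combined liver elevations;
- define whether an AST/ALT increase in Table 9 is judged against ULN or against the patient's baseline;
- make sure that each instruction that allows a restart also gives the dose level.

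The clinical content of each instruction is for the investigators to set. The cost is a text amendment to one section, with IRB approval and notice to the sites. It needs no new tests, visits or patients.

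### Table 11 misprints the platelet bounds for thrombocytopenia: two signs are reversed and three rows omit the thousands, so no platelet count receives its correct grade alone

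*Combined protocol and SAP*

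**What the plan says.** Section 5.4, Table 11, lists four thrombocytopenia rows:

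- "Grade 1: <75,000 mm 3": no change of dose.
- "Grade 2: 50-75 mm 3": interrupt until Grade 1 or better, then resume at the same dose.
- "Grade 3: 25-50 mm 3": the same, with a reduction of one dose level if Grade 3 recurs.
- "Grade 4: >25 mm 3": interrupt until Grade 1 or better, then "initiate ribociclib at the next lower dose level. If toxicity recurs at grade 4: discontinue ribociclib".

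Other parts of the protocol bear on how these rows are read:

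- The general rules at the head of Section 5.4 say that grading follows CTCAE v5.0, that treatment may restart once a toxicity is back to Grade 1 or lower, and that weekly blood counts follow any interruption for hematologic toxicity.
- Section 3.3 gives the eligibility floor for platelets on the full scale, 100,000/mm³.
- Table 10 prints "Grade 4 (ANC < 500/mm 3" for neutropenia, and the anemia rows of Table 11 print "Grade 1: $\geq 10.0$ – LLN g/dL". Both run in the expected direction.

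**The concern.** Grades 2 and 3 fix the direction of the scale: the worse grade has the lower count. Grade 1 must then lie above the Grade 2 range and Grade 4 below the Grade 3 range. The printed signs put Grade 1 below 75,000 and Grade 4 above 25, with no upper limit. Only the Grade 1 row carries the thousands.

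The grade drives three things: whether ribociclib is interrupted, whether it resumes at a lower dose, and whether the patient counts as recovered. If the bounds are wrong, a patient with a dangerously low count could be told to continue or restart, and a patient with a mild reduction could be interrupted and then restarted at a lower dose. Weekly blood counts depend on an interruption, so a patient wrongly placed in Grade 1 would also miss them.

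No other table fills the gap. Table 12 excludes reactions already covered by Tables 5 to 11, and the adverse event log in Appendix 14.6 has no platelet row.

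**Working it through.** No sample-size or power figure is involved. The check applies the four printed bounds, as logical conditions, to every whole-number platelet count *x* per mm³.

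**Inputs.** The four bounds are those of Table 11. The corrected scale uses the table's own cut-points in the order that Grades 2 and 3 imply: Grade 4 if x < 25,000; Grade 3 if 25,000 ≤ x < 50,000; Grade 2 if 50,000 ≤ x < 75,000; Grade 1 if 75,000 ≤ x < LLN. The protocol gives no LLN for platelets. I assume 150,000; 130,000 gives the same result at every example count below.

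**Reading A** (Grades 2 to 4 in thousands, signs as printed): Grade 1 if x < 75,000; Grade 2 if 50,000 ≤ x ≤ 75,000; Grade 3 if 25,000 ≤ x ≤ 50,000; Grade 4 if x > 25,000.

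**Reading B** (strictly literal): Grade 1 if x < 75,000; Grade 2 if 50 ≤ x ≤ 75; Grade 3 if 25 ≤ x ≤ 50; Grade 4 if x > 25.

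**Grades met across the whole range:**

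| Reading A: count | Grades met | Reading B: count | Grades met |
|---|---|---|---|
| 0 to 24,999 | 1 | 0 to 24 | 1 |
| 25,000 | 1, 3 | 25 | 1, 3 |
| 25,001 to 49,999 | 1, 3, 4 | 26 to 49 | 1, 3, 4 |
| 50,000 | 1, 2, 3, 4 | 50 | 1, 2, 3, 4 |
| 50,001 to 74,999 | 1, 2, 4 | 51 to 75 | 1, 2, 4 |
| 75,000 | 2, 4 | 76 to 74,999 | 1, 4 |
| above 75,000 | 4 | 75,000 and above | 4 |

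**Examples against the corrected grade:**

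| Count/mm³ | Reading A | Reading B | Corrected |
|---|---|---|---|
| 20,000 | 1 | 1, 4 | 4 |
| 30,000 | 1, 3, 4 | 1, 4 | 3 |
| 60,000 | 1, 2, 4 | 1, 4 | 2 |
| 80,000 | 4 | 4 | 1 |
| 250,000 | 4 | 4 | none |

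**Counts graded correctly and uniquely.** On reading A a count meets a single grade only below 25,000 (Grade 1 printed, Grade 4 correct) or above 75,000 (Grade 4 printed, Grade 1 or no toxicity correct). On reading B it does so only from 0 to 24 (again 1 against 4) or from 75,000 up (4 against 1 or none). Hence the number of counts from 0 to 149,999 that get the corrected grade and no other is 0 on A and 0 on B. Scaling each of Grades 2, 3 and 4 separately by 1 or 1,000 gives 2 × 2 × 2 = 8 combinations; over 0 to 400,000 the number is 0 for all eight, even when a boundary value may count for either neighboring grade.

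**Restart rule on reading A.** A count below 25,000 is Grade 1 and so qualifies as recovered. A patient who has truly recovered to 90,000 meets only the Grade 4 row.

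**After correction.** With both signs reversed and the thousands restored, every count from 0 to just below LLN falls in exactly one grade, and a count of 200,000 falls in none.

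**The case against.** The strongest reply is that this is a typographical slip that nobody would follow. Section 5.4 ties grading to CTCAE v5.0, and Sections 4.3.10 and 8.7 repeat it. The actions are keyed to grade and escalate sensibly, so a site that grades by CTCAE and reads across gets a coherent instruction. That lowers the risk. But Table 11 prints its own numbers within the same section and nothing says which governs, so the site holds two conflicting scales.

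The most dangerous result, no dose change below 25,000, needs a reader who repairs the thousands but keeps the signs. That is fair: reading A is a possible misreading. The literal reading, however, gives opposite instructions from 76 to 74,999, so it is no safer as a guide.

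The rows stand under a thrombocytopenia heading, so a normal count would not in practice be looked up there. I accept this. The bounds do place every eligible baseline count (100,000 or more) in Grade 4 alone, but that mainly makes the error conspicuous. The 80,000 example survives the objection.

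Exposure is limited. The drugs are prescribed by the patient's own oncologist and follow-up is one cycle. Table 3 does not list thrombocytopenia among the common Grade 3 or 4 events. After baseline there are two scheduled blood counts, at days 8 to 16 and before cycle 2; the second, at day 29 ± 3, can fall as early as day 26, so seven full days off drug are not assured. All this reduces the likelihood of harm without making the thresholds right.

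Finally, the signs might have been damaged in conversion from PDF. That is unlikely: the neutropenia and anemia signs nearby are intact, and three rows also lack the thousands. A look at the page settles it.

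**Conclusion.** The concern holds. The Grade 1 and Grade 4 signs run against the table's own Grade 2 to 3 order, Grades 2 to 4 omit the thousands, and no platelet count gets its correct grade alone on either reading. The conclusion rests on the printed bounds and on the order of Grades 2 and 3; it does not depend on the assumed LLN.

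This should be fixed because the rows are operative dosing thresholds and the only platelet-specific ones in the protocol. The practical risk is modest for the reasons already given.

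The statistical effect is negligible. Sample size and power do not involve platelets, and the laboratory endpoints named in Section 2.4 are neutropenia, ALT and AST. AUC could be affected only if a platelet-driven dose change came before PK sampling, and the first scheduled post-baseline blood count falls in the same day 8 to 16 window as that sampling.

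**What to change.** Reprint the four platelet rows of Table 11 in one unit:

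- Grade 1: 75,000/mm³ up to LLN
- Grade 2: 50,000 to below 75,000/mm³
- Grade 3: 25,000 to below 50,000/mm³
- Grade 4: below 25,000/mm³

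Keep the existing action for each grade, check the bounds against CTCAE v5.0, and send sites a notice of the correction. The cost is four cells of one table and the notice; no new data or procedures are needed.
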